Recently, neutrophils isolated from healthy adult donors were shown to undergo programmed cell death distinct from apoptosis and necrosis to form neutrophil extracellular traps (NETs). NETs are extensive lattices of extracellular DNA and chromatin decorated with anti-microbial proteins and degradative enzymes such as myeloperoxidase and neutrophil elastase (NE). NETs effect extracellular killing of bacteria and fungi. Our laboratory recently characterized impaired NET formation as a novel innate immune deficiency of human newborn infants and showed that PMNs isolated from the cord blood of newborn infants, both term and preterm, demonstrated impaired NET formation and extracellular bacterial killing as compared to PMNs isolated from healthy adults. However, the timing for developmental maturation of newborn infant PMN NET formation remains unknown. Furthermore, while failure of NET formation contributes to the predisposition for and severity of bacterial and fungal infections associated with disorders such as CGD, dysregulated and inappropriately robust NET formation may lead to immune-mediated host tissue damage such as autoimmune small vessel vasculitis.

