Using data generated from the previous version of this IRB application (IRB_00039621 – Neutrophil Extracellular Trap Formation in Newborn Infants at Risk for Necrotizing Enterocolitis – Closed on 11/8/2018), we recently discovered a new regulatory mechanism governing NET formation in the first 2 weeks following birth for neonates, whether term or preterm. Using cord blood samples as well as samples of peripheral blood taken serially from neonates over the first 2 months of life, we recently identified a family of NET-Inhibitory Peptides (NIPs) which circulate in the fetus and neonate and potently inhibit PMNs from forming NETs. These NIPs inhibit NET formation despite stimulation with many NET-generating agonists like LPS, PMA, live gram+ or gram- bacteria, heme, or viruses. We further examined the use of these NIPs in the setting of in vivo sepsis. We found that pretreatment with the NIPs increased survival in the cecal ligation and puncture model of polymicrobial sepsis by 40-60%, with the survival advantage most likely due to decreased NET-mediated inflammatory tissue damage. With these published results (Yost CC, et al., JCI 2016), we are now funded by the NIH to evaluate the use of NIPs as therapeutic agents in preclinical models of neonatal sepsis. These studies will determine regulatory pathways governing NIP expression in the fetus and newborn, NIP mechanism of action, and efficacy in neonatal sepsis.

We hypothesize that NET formation contributes to the pathogenesis of inflammatory syndromes associated with sequelae of prematurity including sepsis, nCLD, ROP, and NEC by inappropriately releasing degradative proteins and tissue destructive enzymes into the inflammatory milieu of the premature infant. We further hypothesize that NIPs may provide protection against NET-associated inflammatory tissue damage.

Study Purposes and Objectives:

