The following study is best described as a prospective, in vitro longitudinal cellular biology study of LPS/PAFstimulated PMNs isolated from the cord and peripheral blood of premature infants at risk for inflammatory sequelae associated with prematurity (including neonatal Chronic Lung Disease (nCLD), early and late onset sepsis, necrotizing enterocolitis (NEC), and retinopathy of prematurity), and from term infants not considered at risk for such sequelae. In the specific case of NEC, we will also assay for NET formation in gastrointestinal tissue samples obtained at the time of surgery for severe NEC in enrolled prematurely born infants if that occurs. Such tissue samples will not be collected for other inflammatory syndromes of prematurity.

These studies are the first of their kind and aim to answer important questions such as the impact of dysregulated NET formation in the pathogenesis of these inflammatory sequelae of prematurity, the regulatory mechanisms

governing NET formation in newborn infants, the role of our newly discovered NET-Inhibitory Peptides (NIPs) as endogenous regulators of NET formation, and their potential use as novel therapeutic agents for dysregulated NET formation.

Inclusion Criteria:

Eligible Patients

1. Preterm infant patients delivered at UUMC and hospitalized in the NICU who are \leq 1500 grams or < 30 weeks gestational age at birth

Cord blood sample obtained at delivery

Peripheral blood sample obtained during IV start under anesthesia at any elective surgeries during the first year of life

2. Term infants delivered at UUMC without complication, either via cesarean section or vaginal delivery.

Cord blood sample obtained at delivery

Heel-prick blood sample obtained at 24 hours of life

Exclusion criteria:

None

Study Procedures:

Recruitment: We will screen charts through a waiver of authorization for potential participants within the University of Utah covered entity. Eligible participants identified through the waiver of authorization will be identified once they are admitted to the hospital for clinical management, with the expectation of delivery during the current hospital admission.

Inclusion/exclusion criteria will be reviewed with the patient's chart and then approached once initial eligibility criteria have been verified.

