After delivery, cord blood will be drawn from the ligated umbilical cord and placenta. For premature deliveries of infants weighing less than 1500 grams, it is estimated that only 5 – 10 mL of cord blood will be obtained. The resuscitation and treatment of a premature infant often requires cord blood specimens for such clinical tests as arterial and venous cord blood gases and blood type and crossmatch in preparation for probable future blood transfusions. These specific clinical cord blood samples will be collected before study blood collection. The residual cord blood will be dripped into sterile 8 mL EDTA-anticoagulated vacutainers, labeled with a study generated patient identifier and transported by [name] or his laboratory technicians to his lab in the Eccles Institute of Genetics for immediate PMN isolation and sample stabilization. This rapid isolation and sample stabilization is necessary given the short life of PMNs *in vitro* and the potential for PMN activation after isolation.

The family will then be approached regarding informed consent as discussed below. If informed consent is obtained, preparations will be made to obtain 3 serial 0.5 ml samples of peripheral blood during the infant's NICU stay. Samples will be collected on the routine lab draw day that most closely correlates with the following days of life (DOL) #: 3, 7, and 14 if still in the NICU at either UUMC or PCH.

Longitudinal samples will be collected into a 0.5 ml EDTA-anticoagulated microtainers and processed in an identical manner to the cord blood already collected. These serial samples will only be collected during routine clinical laboratory draws occurring around the scheduled DOL. No new lines, IVs or heel stick wounds will be started or made for the sole purpose of drawing the scheduled study sample.

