Plasma samples will be obtained from whole blood samples via centrifugation. The aliquots of the plasma will then be run on Tris-Tricine precast gels to resolve proteins and peptides with a molecular weight between 1 and 30 kD. A standard curve with increasing concentration of synthesized NIPs will be run on the same gel and concentration will be determined by comparing the fluorescent intensity of the plasma band to those of the standard curve. Alternatively, we are developing a HPLC/MS2 assay which will use a synthesized "heavy" variant of NIPs to quantify NIP concentration in plasma compared to a known amount of spiked "heavy" NIP.

Qualitative assessment of NET formation in NEC tissue specimens via immunohistochemistry:

NEC tissue specimens processed by pediatric pathology at PCMC and embedded in paraffin will be transported to [name] laboratory and analyzed for NET formation via immunofluorescence. Surgical samples will be sectioned at $5 - 10 \,\mu$ m thickness. NETs will be visualized by examining the colocalization of antibodies against DNA, histones, and neutrophil elastase.

Data Analysis:

NET formation as assessed qualitatively via live cell imaging and immunohistochemistry and quantitatively via extracellular DNA quantitation and neutrophil elastase activity assays.

We anticipate enrolling 40 prematurely born infants in patient group # 1, 20 healthy term newborn infants in patient group # 2 during this study.

Statistical comparisons for the quantitative assays of extracellular DNA and NE activity will be made via one-way ANOVA with post hoc Pairwise Multiple Comparisons made via the Holm-Sidak method.

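### The only planned test, one-way ANOVA, makes no allowance for repeated samples from the same infant: it loses power if sampling times are compared and inflates type I error if samples are pooled

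*Combined protocol and SAP*

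**What the plan says.** In Data Analysis the quantitative assays are to be compared as follows: "Statistical comparisons for the quantitative assays of extracellular DNA and NE activity will be made via one-way ANOVA with post hoc Pairwise Multiple Comparisons", with the Holm-Sidak method. The section anticipates 40 preterm and 20 term infants. The document gives no paired test, infant effect, repeated-measures term or per-infant summary. It also does not say what the levels of the ANOVA are.

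Study Purposes and Objectives describes a "prospective, in vitro longitudinal cellular biology study". The sampling matches that description:

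- **Preterm infants (Phlebotomy, Patient Group #1):** cord blood, then "3 serial 0.5 ml samples of peripheral blood" near DOL 3, 7 and 14, "if still in the NICU at either UUMC or PCH". Inclusion Criteria adds a possible further sample: "Peripheral blood sample obtained during IV start under anesthesia at any elective surgeries during the first year of life".
- **Term infants (Inclusion Criteria; Phlebotomy, Patient Group #2):** cord blood and one later sample, "Heel-prick blood sample obtained at 24 hours of life".
- **Within a sample (Live Cell Imaging):** cells may be stimulated with either of two agonists and read at 1 to 4 hours.

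Background states that "the timing for developmental maturation of newborn infant PMN NET formation remains unknown". Its main hypothesis is between infants: "We hypothesize that NET formation contributes to the pathogenesis of inflammatory syndromes associated with sequelae of prematurity".

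**The concern.** One-way ANOVA treats all values as independent. Holm-Sidak adjusts for the number of comparisons and does nothing about correlation between samples from one infant. Because the factor is unnamed, three uses are possible:

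- **(a) Sampling times as levels.** A within-infant change is judged against between-infant variation, so power is lost. The same holds for agonists or incubation hours run on one sample.
- **(b) Repeated samples pooled as separate values,** for example to compare preterm with term infants, or infants with and without a complication. The standard error is too small and type I error rises.
- **(c) Preterm versus term at one sampling time and one condition.** Each infant contributes one value and the test is roughly valid.

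The plan does not restrict itself to (c). Change over time is not a listed objective, but the serial draws and the open question about maturation make (a) a natural use. Under (a) a moderate change over the first two weeks could be missed although each infant could serve as its own control. Under (b) the main hypothesis could be supported by false positives.

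**Working it through.** **Inputs from the documents:** 40 preterm infants with up to four scheduled samples (cord, DOL 3, 7, 14), and 20 term infants with two. The plan gives no alpha, SD, effect size, power or ICC, so it has no figure of its own to reproduce.

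**Assumptions:** two-sided 5%; total SD 1; ICC 0, 0.3, 0.5 or 0.7, equal for all pairs of times unless stated; complete data; one value per sample.

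**(a) Times as levels, cord versus DOL 14.** One-way ANOVA takes the SE of the change as √(2/40) = 0.224 SD. The true SE is √(2(1−ICC)/40), which at ICC 0.5 is 0.158 SD. The ratio is 1/√(1−ICC) = 1.00 / 1.20 / 1.41 / 1.83 across the four ICCs. The simulated true size of a nominal 5% test is about 5%, 1.9%, 0.6% and under 0.1%.

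Simulated power for a linear rise is below. Power here means the chance that the cord–DOL 14 pair is declared different after Holm-Sidak over the six pairs of times. Each cell shows one-way ANOVA against a within-infant contrast (unstructured covariance, which with complete data equals the paired t test).

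| Rise, cord to DOL 14 | ICC 0 | ICC 0.3 | ICC 0.5 | ICC 0.7 |
|---|---|---|---|---|
| 0.4 SD | 20 v 18% | 16 v 29% | 12 v 43% | 7 v 70% |
| 0.6 SD | 53 v 49% | 51 v 68% | 52 v 85% | 53 v 98% |
| 0.8 SD | 83 v 80% | 87 v 94% | 90 v 99% | 94 v 100% |
| 1.0 SD | 97 v 96% | 99 v 99% | 99 v 100% | 100 v 100% |

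At ICC 0 one-way ANOVA is about 1 to 3.5 points better, because it has 160 − 4 = 156 df against 40 − 1 = 39. If correlation instead decays with time (AR(1), cord–DOL 14 correlation 0.2 / 0.3 / 0.5), power at 0.6 SD is 52 / 51 / 51% against 62 / 69 / 85%.

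**(b) Samples pooled.** For 40×4 = 160 preterm against 20×2 = 40 term values, true over assumed variance is

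[(1+3·ICC)/160 + (1+ICC)/40] / [1/160 + 1/40].

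At ICC 0.5 this is (0.0156 + 0.0375)/0.03125 = 1.70, and the type I error is 2(1 − Φ(1.96/√1.70)) = 13%. Across ICC 0 / 0.3 / 0.5 / 0.7, simulation gives 5 / 10 / 13 / 17%.

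For outcome groups among preterm infants (assumed 10 with and 30 without the outcome, four samples each) the ratio is 1 + 3·ICC, which is 2.5 at ICC 0.5. Simulated type I error is 5 / 16 / 22 / 27%.

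**(c) One value per infant.** Preterm versus term cord blood within a six-level ANOVA keeps 4.8–5.2%.

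**Checks on the alternative:**

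- *Random intercept only.* Under the AR(1) settings, an infant term with one pooled residual has 10–12% type I error for the nominal 5% cord–DOL 14 test. Unstructured covariance has about 5%.
- *Samples missing at random* (assumed 10 of 40 lack DOL 14, and 4 of these also lack DOL 7). Unstructured covariance with Kenward-Roger df keeps 4.7–5.2%. Single-contrast power at 0.6 SD and ICC 0.3 / 0.5 / 0.7 is 81 / 91 / 99%, against 73 / 74 / 80% one-way.
- *Leaving depends on the DOL 7 value* (assumed, about 25% lack DOL 14; ICC 0.3, ICC 0.5, AR(1) 0.3). The one-way change is biased by 0.09 / 0.15 / 0.16 SD and the unstructured one by 0.01 SD or less, though its size is 6.0–6.8%.

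**The case against.** The strongest reply is that the text shows under-specification, not a demonstrated error. Nowhere does it say that serial values will enter one ANOVA together. Pairwise comparisons need only three or more levels, and these could be outcome groups compared at one time, where independence holds. Pooling, and the 10-versus-30 split used to size it, are not in the plan. Times as levels errs on the conservative side, costs nothing at ICC 0 and under 1 point at 1 SD, and concerns a question that is not a listed objective. An unstructured model with Kenward-Roger df may also be more than a study of 40 and 20 infants needs.

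Much of this stands as a limit on the claim. Both harms are conditional, and their sizes depend on an ICC and effects that the documents do not give. The power figures refer to one pair of times with complete data, and a simpler method would be acceptable.

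It does not remove the point. Repeated sampling is built into the design, the one stated test cannot accommodate it, and nothing confines that test to the case where it is valid. If a repeated-measures analysis was intended, the plan should say so.

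**Conclusion.** The concern holds and should be fixed before analysis. The mismatch between repeated sampling and a test for independent values is clear from the text; its size is not, so confidence is medium. At an assumed ICC of 0.3 to 0.7, comparing times by one-way ANOVA gives up 13 to 63 points of power for rises of 0.4 to 0.6 SD, and little for rises near 1 SD. Over the same ICC range, pooling raises a nominal 5% error to 10–17% for preterm versus term, and to 16–27% for the assumed outcome groups. At ICC 0 neither harm arises, and a preterm-versus-term comparison at one time and condition is sound either way.

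**What to change.** In Data Analysis, name the factor and make the infant the unit of analysis. Then:

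- **Main model, for each quantitative assay:** a repeated-measures mixed model with group-by-sampling-time fixed effects, all available scheduled samples, unstructured within-infant covariance and Kenward-Roger df. Estimate the covariance separately by group (4×4 preterm, 2×2 term). No infant supplies both the term 24-hour sample and a DOL 3, 7 or 14 sample, so a single shared matrix would contain three covariances that cannot be estimated.
- **Simpler fallback:** paired within-infant contrasts, and a Welch test for preterm versus term cord blood (simulated size 5.1% with 40 versus 20).
- **Do not rely on a random intercept alone,** because correlation may decay with time.
- **Conditions:** analyse each agonist and incubation time separately; if conditions are compared, pair them within the sample.
- **Outcome groups:** compare by infant, not by sample.
- **Elective-surgery sample:** report separately, since its age is not fixed and few infants may have it.
- **Multiplicity:** keep Holm-Sidak over a short list of contrasts fixed in advance, for example preterm versus term cord blood, and each later sample versus the infant's own cord blood.

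The cost is new wording, slightly more complex modelling, and about 1 to 3.5 points of power if within-infant correlation is near zero. No extra infants, samples or assays are needed.

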For the small subset of at-risk infants who develop NEC requiring surgery at PCH, whether born at UUMC or transported to PCH from a referring institution, we will also obtain fixed and paraffin-embedded gastrointestinal tissue samples at the time of surgery for analysis of NET formation. These samples will be obtained by the pediatric surgical team at the time of exploratory laparotomy and processed by the diagnostic pathology service at PCH. For those infants transported to PCH with surgical NEC from referring institutions, informed consent will be requested upon admission to PCH NICU. If informed consent is obtained, the samples would be processed and transferred by [name] to his laboratory for further analysis.

Patient Group #2: Healthy term infants born at UUMC

After delivery, cord blood will be drawn from the ligated umbilical cord and placenta. For term deliveries at UUMC, it is estimated that approximately 15 - 25 mL of cord blood can be routinely obtained without compromising needs for possible clinical studies such as infant blood-typing. Samples will be dripped into sterile 8

mL EDTA-anticoagulated vacutainers, labeled with a study generated patient identifier and transported by [name] or his laboratory technicians to his lab in the Eccles Institute of Human Genetics for immediate PMN isolation and sample stabilization. Again, this rapid isolation and sample stabilization is necessary given the short life of PMNs *in vitro* and the potential for PMN activation after isolation.

The family will then be approached regarding informed consent as discussed below. If informed consent is obtained, preparations will be made to obtain one additional 1 ml sample of peripheral blood during the infant's heel stick wounding for the 24-hour metabolic screening test performed on all infants before DOL #3 and before hospital discharge. The sample will be collected into 2 0.5 ml EDTA-anticoagulated microtainers and processed in an identical manner to the cord blood already collected. This additional sample will only be collected during the routine 24 – 48-hour metabolic screening laboratory draw. No new lines, IVs or heel stick wounds will be started or made for the sole purpose of drawing the scheduled study sample.

Experimental Procedures:

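### On the natural reading of the plan, unrestricted pairwise testing includes six preterm-term contrasts that mix maturity with postnatal age; define the cells, limit the Holm-Sidak family and report those six descriptively.

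*Combined protocol and SAP*

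**What the plan says.** The inferential plan is one sentence at the end of the Data Analysis section. "Statistical comparisons for the quantitative assays of extracellular DNA and NE activity" are to use "one-way ANOVA with post hoc Pairwise Multiple Comparisons made via the Holm-Sidak method". The section does not say which groups or time points are the levels of the factor, which contrast matters most, or at what alpha. Planned enrolment is given without a calculation: "We anticipate enrolling 40 prematurely born infants in patient group # 1, 20 healthy term newborn infants in patient group # 2".

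The sampling schedule is in the Phlebotomy section.

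- **Preterm infants (Patient Group #1):** cord blood, then peripheral blood on the routine draw day that "most closely correlates with the following days of life (DOL) #: 3, 7, and 14", provided the infant is still in the NICU.
- **Term infants (Patient Group #2):** cord blood, then one sample at the heel stick for the metabolic screen, "performed on all infants before DOL #3 and before hospital discharge". The same section gives the timing of that draw as 24 to 48 hours.

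The Inclusion Criteria list one more preterm sample that the Phlebotomy section does not repeat: "Peripheral blood sample obtained during IV start under anesthesia at any elective surgeries during the first year of life".

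The Background reports a mechanism that regulates NET formation during the first two weeks after birth in term and preterm infants alike. It also says that the timing of developmental maturation of NET formation is not known.

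**The concern.** Cord blood is the only sample that both groups give at the same point. The later preterm samples run to day 14, while the term series stops at one to two days. A one-way layout over group-by-age cells has no term that separates maturity from postnatal age. Unrestricted pairwise testing therefore gives a preterm day 14 versus term heel-stick comparison the same standing as cord versus cord.

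The sponsor's own Background makes postnatal age a plausible driver of the outcome within exactly this window. The design sets at-risk preterm infants against term infants not considered at risk, so a preterm-term difference invites a reading in terms of prematurity. Nothing in the analysis text guards against that. A secondary cost is that every additional contrast tightens the early Holm-Sidak thresholds, including the one that cord versus cord must pass.

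**Working it through.** The plan states no alpha, power, effect size or SD, so there is no sponsor figure to reproduce.

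**Step 1. Count the contrasts.** The scheduled cells are preterm cord, day 3, day 7 and day 14, and term cord and heel stick: 4 + 2 = 6.

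- All pairs: 6 × 5 / 2 = 15.
- Within group: 4 × 3 / 2 = 6 preterm, plus 1 term, gives 7.
- Preterm-term: 4 × 2 = 8.

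| Preterm sample | vs term cord | vs term 24-48 h |
|---|---|---|
| Cord | same sampling point | mixed, source also differs |
| Day 3 | mixed, source also differs | near-matched (about 1-2 days apart, both peripheral) |
| Day 7 | mixed, source also differs | mixed |
| Day 14 | mixed, source also differs | mixed |

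That gives one matched, one near-matched and six mixed contrasts. If the elective-surgery sample is a seventh cell, there are 21 pairs and 5 × 2 = 10 preterm-term contrasts: one matched, one near-matched and eight mixed.

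**Step 2. Can an age effect alone produce a preterm-term difference?** Assume no maturity effect and a postnatal trend in SD units of 0, 0.4, 0.8, 1.2 (preterm) and 0, 0.2 (term). Holm-Sidak over all 15 pairs was simulated with 20,000 runs, cells of 40 and 20, complete samples, and observations treated as independent, as one-way ANOVA does. Rejection rates were:

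- Day 14 vs term cord 93%; day 14 vs term heel stick 79%.
- Day 7 vs term cord 54%; day 7 vs term heel stick 28%.
- Day 3 vs term cord 10%; preterm cord vs term heel stick 2%.
- Day 3 vs term heel stick (near-matched) 2.5%; cord vs cord 0.6%.

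These depend heavily on the assumed trend. For a single 40 versus 20 contrast at the strictest step (alpha 0.00341, 58 df), a pure age difference of 1 SD is declared significant 72% of the time and one of 0.5 SD only 12%.

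**Step 3. Power for cord versus cord.** Assume two-sided family-wise alpha 0.05 and a true difference of 0.8 SD, with 40 and 20 infants and no missing samples.

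- First-step alpha = 1 − 0.95^(1/m): 0.00341 for m = 15 and 0.00568 for m = 9.
- Noncentrality = 0.8 × √(40 × 20 / 60) = 0.8 × 3.651 = 2.921, on 40 + 20 − 2 = 58 df.
- Critical t is 3.053 (m = 15) and 2.872 (m = 9).
- Power is 45.5% (m = 15) and 52.4% (m = 9), a gain of about 7 points. As a single test at 0.05 it would be 81.9%.

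So of the 81.9 − 45.5 = 36.4 points lost between one test and fifteen, taking out the six mixed contrasts recovers 52.4 − 45.5 = 6.9.

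**Step 4. Sensitivity.** Pooling the error over all cells, as the ANOVA would, gives 4 × 40 + 2 × 20 − 6 = 194 df, and first-step power of 48.5% (m = 15) and 55.0% (m = 9). Holm-Sidak steps down, so these are lower bounds for the stated sample sizes. In step-down simulations with a true cord difference of 0.8 SD, cutting the family from 15 to the 8 contrasts that remain when every preterm-term contrast except cord versus cord is dropped gained 4 to 10 points. With 21 pairs, first-step power is 41%.

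**The case against.** The strongest objection is that the six cells are inferred. The analysis text names no factor, and the Experimental Procedures describe stimulation with PAF or LPS over several hours, so stimulus or stimulation time could equally be a factor. That stands: the 15-pair count is conditional on one reading, and the surgery sample would change it. It is also a reason to define the cells, since the text as written excludes none of these readings.

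Several stronger readings are tempting, and the documents do not support them.

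- **That the sponsor will attribute cross-age differences to prematurity.** No section says so, and the study describes itself as longitudinal. Misreading is a risk, not a stated conclusion.
- **That every preterm-term contrast other than cord versus cord is uninterpretable.** Preterm day 3 and the term heel-stick sample are about one to two days apart and both peripheral. That contrast is worth keeping.
- **That the Background establishes a particular age trend.** It gives no direction, size or course within the two weeks. The rejection rates above illustrate assumed trends. They also assume all 40 preterm infants are sampled at day 14, whereas sampling stops for those who have left the NICU.
- **That the mixed contrasts are the main cause of low power, or that a much shorter list is the answer.** Most of the loss comes from correcting for the other comparisons. A five-contrast family would reach 61%, but only by also dropping day 3, 7 and 14 against each other. Those carry no maturity confounding and bear on the sponsor's open question about maturation.

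**Conclusion.** The point holds in a limited form. On the six-cell reading, six of the eight preterm-term contrasts mix maturity with postnatal age, and four of the six also change specimen source. The plan would test them formally alongside the one matched contrast, with nothing to guide their interpretation. The main harm is that an age or specimen difference could be misread as an effect of prematurity. How often depends on a trend the documents do not give.

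The power cost is secondary and modest: about 46% versus 52% at the first step, given a 0.8 SD difference, two-sided family-wise alpha of 0.05 and complete samples from 40 and 20 infants. The contrast count is exact under the six-cell reading; the rest is conditional on these assumptions. This should be changed before analysis, but it does not invalidate the study.

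**What to change.** Amend the Data Analysis section as follows.

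1. Define the cells that enter the analysis, and say whether the elective-surgery sample is one of them. If it is, recount the family.
2. Name preterm versus term cord as the main between-group contrast.
3. Keep preterm day 3 versus the term 24-48 hour sample as a secondary contrast, labelled as near-matched in age.
4. Keep the seven within-group contrasts, including days 3, 7 and 14 against each other. Analyse them as within-infant comparisons (paired or mixed-model), since one-way ANOVA treats repeated samples from one infant as independent. Note that the four of these that involve cord also change specimen source.
5. Apply Holm-Sidak to these 1 + 1 + 7 = 9 contrasts.
6. Report the six mixed contrasts descriptively, and state that they will not be interpreted as effects of prematurity.

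The cost is a change to the analysis text, with no extra samples or infants. The downside is losing formal tests of preterm postnatal samples against term levels at a different age. If the sponsor wants those, it should list them explicitly and state what a difference would and would not show.
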